6. STUDY OBJECTIVES

6.1 Primary Objective

The primary objective of the study is to evaluate the safety profile of JPS within the scope of its intended purpose, when used according to the manufacturer IFU on a representative population of subjects and users.

In order to fulfill this objective, the safety profile of JPS will be assessed by the following endpoints:

- percentage (%) of subjects with at least one serious/not serious adverse event certainly related or possibly related to JPS (primary endpoint) at device removal follow-up (up to 18 months according to site's standard practice);
- percentage (%) of Medical Device Deficiencies (MDDs) at device removal follow-up (up to 18 months according to site's standard practice).

6.2 Secondary Objectives

The secondary objective of the study is to evaluate the clinical performance of JPS within the scope of its intended purpose, when used according to the manufacturer IFU on a representative population of subjects and users.

In order to fulfill these objectives the clinical performance of JPS will be assessed by the two following efficacy endpoints:

- percentage (%) of subjects that reached a satisfactory bone consolidation according to investigator's opinion;
- percentage (%) of subjects that maintained bone correction alignment according to investigator's opinion until device removal.

7. STUDY DESIGN

7.1 Research Type

This is a Post Market Clinical Follow-up (PMCF) study which is retrospective and prospective, observational, single-center, not controlled. All data from patients observation are gathered according to the site standard-of-care.

7.2 Subjects and Sites Numbers

This study will be conducted only on patients with a regular indication for JPS as per IFU (no off-label use will be included): the system is intended in pediatric (excluding newborns) and small stature adult patients. Pediatric patients include infants (greater than 1 month to 1 years of age), children (greater than 1 to 12 years of age) and adolescents (greater than 12 to 18 years of age) and appropriate adults (where according to investigator assessment, the JPS plates fit the treated bone anatomy).

This study includes only one site (monocentric) that is located in Wetter (Germany). The site was chosen for this study due to the number of subject devices already implanted, and the wideness of the indications covered by the surgeries. The site was also positively evaluated by sponsor for the appropriate qualification and competency of the investigator and of the staff, and availability of facilities and equipment.

7.3 Study duration

The follow-up period considered for this study lasts until the second surgery for JPS removal that, with the exception of clinical complications, is usually scheduled between 9 and 18 months after the surgery. (see table 10.2 "Events and Assessments Schedule").

The estimated length of data collection period by the investigator is the time until all data is abstracted from clinical records. The data extraction from clinical record will finish after the plate removal of the last patient is completed.

7.4 End of Study (EOS)

The sponsor has the right to close this observational study at any time. The IEC must be informed.

The study will be terminated prematurely in the following cases:

- If the enrolment rate and data collection are significantly delayed;
- If the sponsor will be informed that the activities related to the study are conducted in conflict with the present protocol;
- Any other reason for the sponsor to deem that the prosecution of the study will harm the subjects' health or rights.

8. SELECTION AND WITHDRAWAL OF SUBJECTS

8.1 Subject Inclusion Criteria

A patient will be eligible for inclusion in the study if:

- had/has a regular indication for surgical intervention with JPS according to the manufacturer's IFU;
- underwent a surgery for bone deformity correction or trauma reconstruction of the lower extremities performed by JPS;
- the clinical data registered in her/him patient chart are sufficient to assess the safety and efficacy endpoint of the study (for retrospective patients);
- patient (or his/her legally acceptable representative) is capable of understanding the content and is willing to sign the Informed Consent Form (ICF);
- patient is willing and able to participate in the data collection and comply with the protocol requirements

8.2 Subject Exclusion Criteria

A Patient will be excluded from participation in the study if he/she:

- had/has a medical condition that is a contraindication according to the manufacturer's instruction for use leaflet;
- had/has a concomitant not permitted device which cannot be safely removed;
- patient for whom there are other concurrent medical or other conditions that in opinion of the participating investigator may prevent participation or otherwise render patient ineligible for the study.

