9.2 Concomitant Treatments

9.2.1 Permitted Concomitant Treatments (Medications and Therapies)

K-wires and any other concomitant devices, i.e. bone screws, that were applied to fix any bone fragments but that were not considered critical for the maintenance of treated bone alignment, are permitted during the study. It is understood that, any necessary medical devices applied on any other bones than the one treated by JPS are permitted as well.

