9.2.2 Not Permitted Concomitant Devices

Not permitted devices on the same JPS-treated bone: others plates providing fixation; external fixators; intramedullary nails or elastic nails.

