13 ANALYSIS POPULATION

The classification of the implants based on compliance with the screening criteria is defined below:

- **Evaluable implants** are defined as all implants who meet all inclusion criteria and none of the exclusion criteria described in the protocol.
- **Non-evaluable implants** are defined as all implants who fail to meet any of the inclusion criteria or meet any of the exclusion criteria.

The CRF contains the screening criteria information in the form of a binary variable (Yes/No) for each item described.

Analyses will be performed on evaluable implants.

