24.1 SATISFACTORY BONE CONSOLIDATION

The categorical variables to be described are:

- Number of Implants that reached a satisfactory bone consolidation according to investigator's opinion in any visit
- Number of patients that reached a satisfactory bone consolidation according to investigator's opinion in any visit or implant

The descriptive statistic (Mean, SD, Median, Q₁, Q₃, Min, Max) will be shown for the following continuous variable:

- Time to full consolidation from surgery (months), per implant, considered at the first visit in which the answer is "Yes" in "Has been reached a satisfactory consolidation?" variables. Calculated as date of first satisfactory consolidation minus date of surgery.

A list will be made to identify possible outliers from the "time to full consolidation from surgery" in order to verify if there are any. In case any outliers descriptive of "time to full consolidation from surgery" will be repeated without the outlier data.

A list with satisfactory bone consolidation variables will be shown.

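### The exclusion criterion catches a device barred by Protocol 9.2.2 only if it cannot be safely removed, so an implant that healed alongside a since-removed listed device is evaluable and its healing is credited to JPS

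*Protocol*

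**What the plan says.** **Prohibition.** Protocol 9.2.2 reads: "Not permitted devices on the same JPS-treated bone: others plates providing fixation; external fixators; intramedullary nails or elastic nails". It says nothing about whether the device can be taken off.

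**Permission.** Protocol 9.2.1 allows K-wires and other devices such as bone screws "that were not considered critical for the maintenance of treated bone alignment, are permitted during the study". It also allows devices on other bones.

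**Exclusion criterion.** Protocol 8.2, with the same wording in the Synopsis and SAP 12, excludes a patient who "had/has a concomitant not permitted device which cannot be safely removed".

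**Analysis set.** Under SAP 13, evaluable implants "are defined as all implants who meet all inclusion criteria and none of the exclusion criteria described in the protocol". The same section states: "Analyses will be performed on evaluable implants". On data capture it states: "The CRF contains the screening criteria information in the form of a binary variable (Yes/No) for each item described".

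**Endpoints.** SAP 24.1 reports the "Number of Implants that reached a satisfactory bone consolidation according to investigator's opinion in any visit", with a matching count by patient. SAP 24.2 counts implants and patients in deformity cases whose correction is maintained to the last visit performed. Neither count depends on what other fixation was on the bone.

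**The concern.** Consolidation and held alignment are evidence about the plate only if the plate was the fixation. Protocol 9.2.2 appears to be written to secure that. The criterion that decides who is analysed asks a different question: whether the extra device could be taken off safely. For a retrospective case, already treated and explanted, the answer says nothing about what held the bone while it healed.

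At stake is whether the two efficacy percentages, which support the device's clinical evaluation, describe JPS alone or JPS plus a second fixation that the protocol rules out.

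**Working it through.** The plan gives no figure on this point, so there is none to reproduce. The check is a reading of the rules, followed by a sizing under stated assumptions.

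**Step 1: follow one case through the rules.** Take a retrospective implant that had an external fixator on the same bone during healing, taken off before chart review.

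| Rule | Question it asks | Result |
|---|---|---|
| Protocol 9.2.2 | Listed device on the JPS-treated bone? | Yes: not permitted |
| Protocol 8.2, Synopsis, SAP 12 | Not-permitted device that cannot be safely removed? | No: it was removed, so not excluded |
| SAP 13 | All inclusion criteria and no exclusion criterion met? | Evaluable, if the other criteria are met |
| SAP 24.1, 24.2 | Consolidated? Correction maintained? | Counted for JPS if yes |

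**Step 2: look for another rule that stops it.**
- No section requires a removable listed device to be removed, sets a time for it, or says how the implant is classified if the device stayed on.
- Protocol 10.1 says the study does not alter normal practice, and the retrospective cohort has already had JPS removal.
- Protocol 14.5 has deviations reported and discussed, but does not take them out of the analysis. The SAP has no per-protocol set.
- SAP 17.1 describes plate size and type and screw counts. No SAP table covers concomitant devices.

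**Step 3: size for consolidation.** The documents give no consolidation rate and no number of such implants. Assume that 90% of implants consolidated (h of n) and that k implants with a listed device all healed. Then:
- dropped from the analysis: (h − k)/(n − k)
- kept, but not attributed to JPS: (h − k)/n

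Intervals are Clopper-Pearson at the SAP's 95.2% level.

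| n | h | k | Dropped (95.2% CI) | Not attributed |
|---|---|---|---|---|
| 30 | 27 | 0 | 27/30 = 90.0% (73.3 to 97.9) | 90.0% |
| 30 | 27 | 1 | 26/29 = 89.7% (72.5 to 97.9) | 26/30 = 86.7% |
| 30 | 27 | 3 | 24/27 = 88.9% (70.7 to 97.7) | 24/30 = 80.0% |
| 30 | 27 | 6 | 21/24 = 87.5% (67.5 to 97.4) | 21/30 = 70.0% |
| 40 | 36 | 1 | 35/39 = 89.7% | 35/40 = 87.5% |
| 40 | 36 | 3 | 33/37 = 89.2% | 33/40 = 82.5% |
| 40 | 36 | 6 | 30/34 = 88.2% | 30/40 = 75.0% |

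One implant in 30 is worth 1/30 = 3.3 points when its healing is not attributed to JPS, but only 90.0 − 89.7 = 0.3 points when it is dropped.

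**Step 4: direction for the primary safety endpoint.** Under Protocol 11.1.3, an event that another device could also explain can still be rated Possible, and Possible events count in the primary endpoint. Keeping a co-fixated implant may therefore add a counted event or add an event-free case. The direction cannot be told from the documents.

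**The case against.** The best defence is that a removable device is meant to be removed, so the criterion and 9.2.2 agree in spirit. That is not written, and it cannot be applied to treatment already completed. The general criteria on complying with the protocol and on investigator discretion (8.1, 8.2) could be used to screen such a case out. They name no device and require nothing specific, and for retrospective cases they would be applied once the outcome is known.

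Two objections stand. No such implant is shown to exist. And the point covers only devices on the 9.2.2 list, because 9.2.1 permits some other fixation on the same bone.

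A reader might also infer four stronger things that the documents do not support:

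- **Rescued failures drop out.** A nail or plate added after JPS failed would have to be both concomitant with JPS and not safely removable; merely being left in is not enough, and a device that replaces JPS is not concomitant. Prospective eligibility is checked at V0, and nothing says a later device reopens it. What remains is that the criterion has no time anchor, an ambiguity for retrospective cases.
- **Every error favours the device.** This fails for the primary endpoint (step 4).
- **One case can decide the 15% safety criterion.** The upper 95.2% limit is 17.4% for 1/30 and 12.1% for 0/29, but that contrast needs the rescued-failure reading and a chosen count. At 40 implants, one per subject, 1/40 gives 13.3% and 0/39 gives 9.1%, both below 15%.
- **Nothing would be visible.** SAP 16.1 shows non-evaluable patients with reasons, Protocol 14.5 requires deviations to be reported, and SAP 23.1.4 lists adverse events. The gap is the missing table of concomitant devices.

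**Conclusion.** The point holds for 9.2.2-listed devices. As written, a retrospective implant that healed with such a device, since taken off, is evaluable despite the prohibition, and its consolidation and maintained correction are credited to JPS. For these descriptive efficacy endpoints the bias is towards the device, given that the implant healed. For the primary safety endpoint its direction is undetermined.

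The size is unknown because the number of such implants is unknown. On the assumed 27/30, one healed case makes a difference of 0.3 points if dropped and 3.3 points if not attributed to JPS. Three cases not attributed would lower the figure to 80.0%. The effect is small if such cases are rare or simply dropped, and material only if there are several. This is a correctable mismatch in the analysis-set definition and does not show that the results are wrong.

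**What to change.** 1. Reconcile the Synopsis exclusion criteria, Protocol 8.2 and 9.2.2, and SAP 12 and 13. Which devices are acceptable in practice is for the sponsor and the investigator to settle; the items below concern the analysis only.
2. In SAP 13, classify each implant by whether a 9.2.2-listed device was on the same bone at the index JPS surgery, not by whether it could be removed.
3. Report consolidation, maintained correction and device-related adverse events with and without such implants. This avoids having to choose a single attribution rule.
4. State that a listed device added after the index surgery does not make an implant non-evaluable, and list those cases.
5. Add a table of 9.2.2-listed devices on the treated bone, for example in SAP 17.1. It would show whether the problem occurs at all.

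**Cost.** Wording changes, one table and one repeat of the main summaries. A few implants may become non-evaluable. Protocol 10.2.2 names JPS components and the surgery but not concomitant devices, and Protocol 14.6 limits the analysis to eCRF data and rules out additional data collection. If the eCRF has no field for these devices, one item must be added or abstracted from the operative notes, and the protocol must allow for it.

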8.3 Subject Withdrawal

Subjects must be withdrawn once he/she withdrew his/her consent for participation in the study (applicable for prospective cohort).

In all cases, subjects are withdrawn must be recorded in detail in the eCRF. Should the clinical investigation be discontinued prematurely, all clinical investigation materials (complete, partially completed and empty CRFs) will be retained.

9. TREATMENT OF SUBJECTS

9.1 Study Investigational Product(s)

General information

The JPS is a complete plating system designed to address the specific demands of advanced deformity and trauma reconstruction of the lower extremities in pediatric population and small stature adults. The system is intended for internal fixation and stabilization of fractures, osteotomies, mal-unions and non-unions of long bones of the lower limb.

Classification and Regulatory Status

The JPS is a Class IIb medical device according to the MDD 93/42.

9.1.1 Description of the Investigational Products

Device Description and Specifications

The JPS consists of 3 different plate sizes, identified as 3.0 mm, 3.5 mm and 5.0 mm, available in different lengths according to the anatomical application. Plates have been designed to accept bone screws of suitable diameters. Bone screws are available in 3 different diameters (3.0 mm, 3.5 mm and 5.0 mm corresponding to the plate size), they can be used with different lengths as well as in locking and non-locking options. Application and removal of the JPS can be performed using Orthofix general orthopedic instrumentation.

Materials

The implants are made from implant grade stainless steel AISI 316 LVM, conforming to ASTM F138 and ISO-5832.

9.1.2 Delivery and Storage Requirements

This study is a post-market investigation, therefore the dispensation of the device is through the standard market distribution. The device storage, accountability and preparation for use is under responsibility of the clinical site.

9.2 Concomitant Treatments

9.2.1 Permitted Concomitant Treatments (Medications and Therapies)

K-wires and any other concomitant devices, i.e. bone screws, that were applied to fix any bone fragments but that were not considered critical for the maintenance of treated bone alignment, are permitted during the study. It is understood that, any necessary medical devices applied on any other bones than the one treated by JPS are permitted as well.

9.2.2 Not Permitted Concomitant Devices

Not permitted devices on the same JPS-treated bone: others plates providing fixation; external fixators; intramedullary nails or elastic nails.

10. STUDY PROCEDURES

10.1 Description of Procedures

Throughout the pre-study meetings, it was assessed and confirmed that the clinical data collected for the study purpose are part of the standard clinical practice for the participating investigational site. As this is an observational study, there are no change or influence to the normal clinical practice of the investigator and patients, and no interference with the local hospital standard of care guidelines and/or the internal therapeutic protocols set and established at the investigational site.

For retrospective study cohort, who have previously had JPS implemented and follow-up assessment and JPS removal is done, the investigators shall purely collect clinical data from the medical record of the subjects, concerning the screening criteria, the surgery (MD application) and 4 following events: hospital discharge, first post-application control, bone consolidation assessment and device removal. Data from patients observation are collected according to the site practice. Please note that the term "Visit" and "Event" are used as synonyms to indicate the steps collected by this observational study.

Patients from the prospective cohort, who have undergone JPS implantation, will be observed in accordance with Table 10.2 or until patient withdrawal.

The patients' data are systematically collected by the investigator in the eCRF provided by Sponsor.

10.2 Description Event by Event

10.2.1 V0: Screening and Baseline

Prospective patients who meet the eligibility criteria will be enrolled in the study. Patients who agree to enter the study must sign the approved Informed Consent Form. Consented patients will have performed assessments as outlined in this protocol.

During the screening the investigator will evaluate the eligibility of the patients, checking all inclusion and exclusion criteria. Only those patients who meet all inclusion and exclusion criteria will be enrolled in the study. For each JPS implant a unique case number will be assigned (ID), and reported in the eCRF. Considering that each patient can contribute for more than one JPS implant: one patient can have more than one ID. In the eCRF the IDs are linked to the first ID assigned to the same patient by the clinical site. The patients not enrolled for non compliance will be considered as screening failures and will not be entered in the eCRF. Only for the enrolled patient, the Investigator will collect the demographic data and the medical history of the patient including information concerning the limb to be treated with JPS (baseline) such as the radiographic images and clinical examination.

10.2.2 V1 (Day 0): Surgery

The investigator will collect information regarding the applied components of the JPS and the surgical intervention itself, including the intraoperative application time of fluoroscopy. The investigator will also collect X-ray images to assess the treatment outcome, and the medication prescribed after the surgery. From this visit and for the rest of the visits, the

Investigator will collect information about adverse events (AEs) and medical device deficiency (MDD).

10.2.3 V2 (1 Week +/- 2 days): Hospital discharge

The investigator to collect information regarding changes in the concomitant medication, WBI; ROM (when available in the medical file) AEs and MDDs, if any.

10.2.4 V3 (6 Weeks +/- 2 weeks): 1st control visit

The investigator will collect information regarding changes in the concomitant medication, AEs and MDDs, if any, about the functional recovery of the treated limb (by the means of the ROM and the WBI when available), and about the bone healing consolidation by X-ray images.

10.2.5 V4 (6 to 9 Months): bone consolidation

The investigator will collect information regarding changes in the concomitant medication, AEs and MDDs, if any, about the functional recovery of the treated limb (by the means of the ROM and the WBI when available), and about the bone healing consolidation process by X-ray images.

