EXCLUSION CRITERIA	
A patient will be excluded from participation in the study if he/she:
 
 • had/has a medical condition that is a contraindication according to the manufacturer's instruction for use leaflet; • had/has a concomitant not permitted device which cannot be safely removed; • patient for whom there are other concurrent medical or other conditions that in the opinion of the participating investigator may prevent participation or otherwise render patient ineligible for the study.
COMPARATIVE DEVICE	Not applicable (the study is not controlled)
PERMITTED CONCOMITANT DEVICE	K-wires and any other concomitant devices, i.e. bone screws, that were applied to fix any bone fragments but that were not considered critical for the maintenance of treated bone alignment, are permitted during the treatment. It is understood that any necessary medical devices applied on any other bones other than the one treated by JPS are permitted as well.
QUALITY OF LIFE (QOL)	
A QOL questionnaire is not performed in the normal clinical practice of the site participating this study. Provided clinical data will be retrospectively collected, it will not be possible to report a QOL questionnaire as a study result. Anyway, when available, the range of motion (ROM) of the treated limb and the weight bearing index will be collected and assessed as representative variables for the evaluation of the QOL of the enrolled Subjects.

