auditor and regulatory authorities, and that the information will be used during the analysis of the results.

The data gathered for this group at the visits and assessment during the follow-up period, will be systematically collected by the investigator in eCRF.

Subjects will not undergo additional visits nor invasive or burdensome procedures additional to those already performed under the normal clinical practice. The scope of data collection is limited to the available data in the patients' charts.

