16.7 PRE-OP ROM AND WB BY IMPLANT

The categorical variables to be described are, N and (%):

- Pre operative Weight-bearing Grade (Non-weight-bearing (NWB) / Toe-touch weight-bearing (TTWB) / Partial weight-bearing (PWB) / Full weight-bearing (FWB))
- Which Range of Motion are available for this patient?
 - Knee Flexion
 - Knee Extension
 - Hip Flexion
 - Hip Extension
 - Hip Abduction
 - Hip Internal Rotation
 - Hip External Rotation
 - Ankle Joint Dorsiflexion
 - Ankle Joint Plantarflexion
 - None

The descriptive statistic (Mean, SD, Median, Q₁, Q₃, Min, Max) will be shown for the following continuous variables:

- ROM Knee Flexion
- ROM Knee Extension
- ROM Hip Flexion
- ROM Hip Extension
- ROM Hip Abduction
- ROM Hip Internal Rotation
- ROM Hip External Rotation
- ROM Ankle Joint Dorsiflexion
- ROM Ankle Joint Plantarflexion

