20.3 ROM AND WB AT BONE CONSOLIDATION ASS

The categorical variable to be described is, N and (%):

- Current Weight-bearing Grade (Non-weight-bearing (NWB) / Toe-touch weight-bearing (TTWB) / Partial weight-bearing (PWB) / Full weight-bearing (FWB))

The descriptive statistic (Mean, SD, Median, Q₁, Q₃, Min, Max) will be shown for the following continuous variables:

- ROM Knee Flexion
- ROM Knee Extension
- ROM Hip Flexion
- ROM Hip Extension

- ROM Hip Abduction
- ROM Hip Internal Rotation
- ROM Hip External Rotation
- ROM Ankle Joint Dorsiflexion
- ROM Ankle Joint Plantarflexion

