21.4 ROM AND WB AT DEVICE REMOVAL

The categorical variable to be described is, N and (%):

- Current Weight-bearing Grade (Non-weight-bearing (NWB) / Toe-touch weight-bearing (TTWB) / Partial weight-bearing (PWB) / Full weight-bearing (FWB))

The descriptive statistic (Mean, SD, Median, Q₁, Q₃, Min, Max) will be shown for the following continuous variables:

- ROM Knee Flexion
- ROM Knee Extension
- ROM Hip Flexion
- ROM Hip Extension
- ROM Hip Abduction
- ROM Hip Internal Rotation
- ROM Hip External Rotation
- ROM Ankle Joint Dorsiflexion
- ROM Ankle Joint Plantarflexion

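### Range of motion is recorded only when available and summarised visit by visit with no within-implant change, so a reader comparing visits can mistake a change in who was measured for a change in function (minor; no endpoint affected)

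*Protocol*

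**What the plan says.** **Purpose.** Protocol 10.2.4 to 10.2.6 (first control, bone consolidation, device removal) link ROM to recovery of the treated limb. At bone consolidation the information is "about the functional recovery of the treated limb (by the means of the ROM and the WBI when available". The synopsis explains that no quality-of-life questionnaire is available and that "when available, the range of motion (ROM) of the treated limb and the weight bearing index will be collected and assessed as representative variables" for quality of life.

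**Availability.** At discharge (10.2.3) the protocol lists "WBI; ROM (when available in the medical file) AEs and MDDs, if any", without mentioning recovery. Section 13.2 adds: "The scope of data collection is limited to the available data in the patients' charts". Table 10.2 schedules ROM at screening and at V2 to V5.

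**Analysis.** SAP 16.7, 18.2, 19.3, 20.3 and 21.4 list nine movements of the hip, knee and ankle at each of five time points. Each list is introduced as in SAP 20.3: "The descriptive statistic (Mean, SD, Median, Q₁, Q₃, Min, Max) will be shown for the following continuous variables". No section defines a change from pre-op, a common set of implants or a rule for missing ROM. SAP 13 takes all evaluable implants, defined by the screening criteria.

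**Display of coverage.** Only the pre-op section has the item "Which Range of Motion are available for this patient". SAP 14 shows total and valid percentages for qualitative variables only, and its list of statistics for quantitative variables leaves out n. Protocol 12.4 includes n.

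**The concern.** Recovery is a change over time in the same limb. The plan's ROM output is five unlinked cross-sections, and the set of implants behind each can differ. Routine charts may record ROM more often in some patients than in others, for example in cooperative and mobile patients, or when motion is a worry. If that pattern differs between visits, the means can drift although no limb has changed.

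The stake is limited but real. ROM and weight bearing are the only variables the protocol offers in place of a quality-of-life measure, in a study meant to support the benefit/risk case for the device. Weight bearing has a per-implant summary in SAP 24.3 (time to full weight bearing). ROM has nothing comparable. The pre-op value that would allow one is already collected for each implant when the chart holds it.

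**Working it through.** The plan states no figure on this point, so there is none to reproduce. The documents supply the structure: five time points, nine movements, ROM only when available, and 30 to 40 implants. **All ROM values and coverage rates below are assumptions.**

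**1. Formula.** Let m be the share of implants measured at a visit and g the mean of the measured minus the mean of the unmeasured. The error in that visit's mean, against the mean over all evaluable implants, is (1 − m) × g. This is the error in one visit's level. The artefact in a comparison of two visits is a difference:

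(1 − m_later) × g_later − (1 − m_pre) × g_pre

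One visit's term, for a range of assumptions:

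| Share measured | g = 10° | g = 20° |
|---|---|---|
| 80% | 2° | 4° |
| 70% | 3° | 6° |
| 50% | 5° | 10° |

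These become artefacts in a comparison only so far as the other visit does not carry the same term.

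**2. Count example, no limb changing.** Take 30 implants, 15 at 80° and 15 at 110°, all measured pre-op: mean 95°.
- Five stiff limbs lack a later value: (10 × 80 + 15 × 110)/25 = 98.0°, an apparent gain of 3.0°.
- Five mobile limbs lack it instead: (15 × 80 + 10 × 110)/25 = 92.0°, an apparent loss of 3.0°.
- The paired change is 0 in both cases.

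**3. Different selection at the two visits.** Take 40 implants, mean 90°, SD 20°, no true change. Pre-op coverage is 90% at random; later coverage is 80% above 90° and 40% below.
- Each half lies on average 20 × √(2/π) = 15.96° from the mean.
- The later measured mean is off by (0.8 × 15.96 − 0.4 × 15.96)/(0.8 + 0.4) = 5.3°.
- The pre-op error is 0 on average, so the tables show a gain of 5.3°. A simulation with 20,000 repeats also gives 5.3°, and a paired change of 0.0°.
- Expected pairs: 40 × 0.9 × 0.6 = 21.6.

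**4. Same selection at both visits.** With 80%/40% coverage by the same patient trait pre-op and later, both terms are 5.3° and the difference is 0.0°, as in the simulation.

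**5. Values missing purely at random.** With 30 implants measured pre-op, SD 20° and no change, the chance shift has SD 20 × √(1/n − 1/30): 2.6° with 20 measured later and 3.7° with 15.

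**6. What pairing does not repair.** Let individual true changes vary with mean 0 and SD 15°.
- Later coverage as in step 3. The later SD is √(20² + 15²) = 25°, so the unpaired artefact is 25 × √(2/π)/3 = 6.6°. The paired estimate keeps the share 15²/25² = 0.36 of it: 0.36 × 6.6 = 2.4°.
- Later coverage of 80% if motion was lost and 40% otherwise. Both estimates are off by −15 × √(2/π)/3 = −4.0°.

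**7. Precision.** In step 3 with 8° of within-implant measurement noise, the simulated SD of the estimate is 2.5° paired and 3.6° unpaired.

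**The case against.** The strongest reply is that no such analysis is planned. The SAP names no ROM trend, test or conclusion, and the protocol says only that the information is collected. ROM is not among the safety or efficacy endpoints, and the limit to chart data is stated openly. All of this stands and sets the priority.

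Three stronger readings are tempting, and the documents do not support them.
- *The plan intends the tables to be read as a trend.* The recovery wording makes that reading natural, but it is an inference.
- *The ROM results will be wrong by about 5 degrees.* That figure needs random pre-op coverage and value-dependent later coverage. Nothing in the documents shows this asymmetry. A stable trait such as cooperation would act at both visits and largely cancel.
- *Coverage will be hidden.* Protocol 12.4 already calls for n with every quantitative variable. The omission in SAP 14 is a mismatch with the protocol, easily repaired.

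It is also fair to object that pairing can be oversold: step 6 shows error remaining after pairing, in one case undiminished. The case for pairing is narrower. It removes the artefact of a changing measured set, and it was more precise in the noise runs.

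**Conclusion.** The point holds as a minor one about a supportive, descriptive analysis. The ROM tables cannot on their own carry a statement about recovery, because nothing keeps the implants comparable from visit to visit. The primary safety result and both efficacy endpoints are untouched.

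Size and direction cannot be known from the documents. Under the assumed values, the artefact is about 5° when selection differs between visits as in step 3 and near 0 when it is the same. It can have either sign. With values missing at random, it is chance variation with SD of about 3 to 4° when half to two thirds of 30 implants are measured later. One generic ROM with mean 90° and SD 20° stands here for nine movements, so these figures show the mechanism and are not a forecast.

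**What to change.** - In SAP 18.2, 19.3, 20.3 and 21.4 add, for each movement, the within-implant change from the SAP 16.7 pre-op value, among implants with both values, with the number of pairs.
- At every visit report the number measured out of evaluable implants for each movement, and restore n to the list for quantitative variables in SAP 14 to match protocol 12.4.
- Keep the per-visit summaries as description. Rest any ROM-based statement on recovery on the paired change.
- Add a sentence that the paired change does not correct for selection of which implants have both values.

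**Cost.** SAP wording and derived change variables; no new data, visits or procedures. Nine movements at four post-operative visits give up to 36 change summaries, some with few pairs. The paired n falls wherever the pre-op value is missing.
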